#### **6.5.1.2. Patient eDiary**

All women enrolled in the study will continue to use the patient eDiary dispensed in the parent study (see [Appendix 2](#)). Patients will complete daily eDiary entries including NRS pain scores, menstruation information, analgesic drug use, date and time of study drug administration, and sB&B scale scores.

The site should review the eDiary data at every visit.

#### **6.5.1.3. Endometriosis Health Profile-30**

The EHP-30 is used to evaluate the functional impact and the quality of life of patients with endometriosis (see [Appendix 3](#)). Patients will complete the EHP-30 questionnaire at the site at visits indicated in [Section 1.1](#) before other types of study procedures, such as blood draws and physical examinations, are performed. The EHP-30 will be completed on a tablet device at the study site.

#### **6.5.1.4. European Quality of Life Five-Dimension Five-Level Scale**

The EQ-5D-5L is a standardized instrument for use as a measure of health outcomes (see [Appendix 4](#)). Mobility, self-care, usual activities, pain/discomfort, and anxiety/depression are each assessed on a 5-level categorical scale.

---

Patients will complete the EQ-5D-5L questionnaire at the site at visits indicated in [Section 1.1](#) before other types of study procedures, such as blood draws and physical examinations, are performed. The EQ-5D-5L will be completed on a tablet device at the study site.

#### **6.5.1.5. Patient Global Assessment and Patient Global Impression of Change**

These simple questions are used by the patient to qualitatively describe severity of pain or effects on function (PGA) or impression of change in pain severity (PGIC) (see [Appendix 5](#)) on a schedule described in the Schedule of Activities ([Section 1.1](#)). Patients should answer these questions before other types of study procedures, such as blood draws and physical examinations, are performed. The PGA for pain severity and the PGIC will be completed on a tablet device at the study site. The PGA for function will be completed on a paper questionnaire at the study site.

#### **6.5.1.6. Endometriosis Health Profile Work Domain**

This 5-question paper questionnaire will be completed by the patient to describe the effects of endometriosis on their work ([Appendix 6](#)). Patients will complete the EHP Work Domain questionnaire at visits indicated in [Section 1.1](#) before other types of study procedures, such as blood draws and physical examinations, are performed. The EHP Work Domain will be completed on a paper questionnaire at the study site.

### **6.5.2. Safety-Related Procedures**

#### **6.5.2.1. Weight**

Patients should have weight and height measured while wearing indoor clothing and with shoes removed.

#### **6.5.2.2. Vital Signs**

Vital signs, including blood pressure, heart rate, and temperature, should be measured in the seated position after 5 minutes of rest.

#### **6.5.2.3. Physical Exams**

A complete physical examination will include head, ears, eyes, nose, mouth, thyroid, skin, heart and lung examinations, lymph nodes, gastrointestinal, skeletal, and neurological systems. All subsequent physical examinations should focus on signs and symptoms reported by the patient to assess for clinically significant changes from the Baseline assessment.

#### **6.5.2.4. Clinical Laboratory Samples**

All protocol-required laboratory assessments must be conducted in accordance with the Study Laboratory Manual and the protocol Schedule of Activities (see [Section 1.1](#)). Laboratory requisition forms must be completed and samples must be clearly labelled with the Patient ID

number, protocol number, site/center number, and visit date. Details for the preparation and shipment of samples will be provided. Reference ranges for all safety parameters will be provided to the site by the central laboratory.

The samples collected for clinical laboratory tests are listed in [Table 6-1](#).

**Table 6-1 Clinical Laboratory Tests**

Chemistry	Hematology	Urinalysis
Potassium	White blood cell count	Protein
Chloride	White blood cell differential	Glucose
Bicarbonate	Red blood cell count	Blood
Blood urea nitrogen	Hemoglobin	Urobilinogen
Creatinine	Hematocrit	Bilirubin
Glucose	Mean corpuscular volume	Color and clarity
Calcium	Platelet count	pH
Phosphate	Red blood cell morphology	Leucocyte esterase
Magnesium		Ketones
Sodium		Nitrite
Albumin		Specific gravity
Creatine kinase		Urine Microscopy (reflex testing based on abnormal urine analysis)
Hemoglobin A1c		
Bilirubin total		
Alanine aminotransferase		
Aspartate aminotransferase		
Gamma-glutamyl transferase		
Alkaline phosphatase		
Hormones	Lipids	Pregnancy
Estradiol	Total cholesterol	Pregnancy test (human chorionic gonadotropin)
	Low density lipoprotein	
	High density lipoprotein	
	Triglycerides	

The central laboratory will perform laboratory tests for chemistry, hematology, urinalysis, and serum hormone levels. Each study site will conduct urine pregnancy tests locally.

All laboratory tests with values that are considered abnormal and clinically significant during participation in the study or within 30 days after the last dose of study drug should be repeated until the values return to normal, baseline, or have stabilized. Abnormal values, determined to be clinically significant, should be reported as adverse events.

The investigator will maintain a copy of the reference ranges (with the record of the reference ranges) for the laboratory or laboratories used.

#### **6.5.2.5. Electrocardiograms**

ECGs (12-lead) will be obtained at the time points described in the Schedule of Activities (Section 1.1). ECGs will be measured using standardized equipment provided by the central core laboratory with the patient in a semi-supine or supine position after 5 minutes of rest. The ECGs will be assessed by central review and a report provided to the site. The investigator or sub-investigator (or a qualified individual at the investigational site) will interpret the ECG report provided by the central reviewer using one of the following categories: normal or abnormal. The investigator or sub-investigator will judge if any of the findings are clinically significant.

#### **6.5.2.6. Bone Mineral Density**

Bone mineral density is determined using DXA scanning and will be assessed at the lumbar spine (L1, L2, L3 and L4), total hip, and femoral neck (same leg within each patient) at the time points described in the Schedule of Activities (Section 1.1). The scans will be read by the central imaging laboratory in accordance with the imaging charter. Training, quality review, and readings will be done by a central radiology laboratory as described in the central radiology charter for bone mineral density.

Throughout the study, the same DXA apparatus will be used at each site and operated in the same scan mode for all scans for an individual patient and should be the same as used for the patient during the parent study (MVT-601-3101 and MVT-601-3102). The central core imaging laboratory will collect and evaluate all DXA scans for acceptability. Bone mineral density changes for individual patients will be monitored by the central imaging laboratory over the course of the study.

Patients with a bone mineral density loss of  $> 3\%$  at lumbar spine or total hip at their Week 52/Early Termination visit (or most recent scan if the Week 52/ET scan was not done) relative to parent study Baseline measurement will undergo another bone densitometry scan at  $6 (\pm 1)$  months and will be contacted to obtain information about medications and conditions (eg, pregnancy) that might affect bone mineral density through the time of the follow-up bone densitometry. The follow-up bone densitometry will be submitted for central reading.

Patients who experience a bone mineral density loss from the parent study Baseline of  $\geq 7\%$  at any of the anatomical sites assessed will be discontinued from the extension study and will undergo another bone densitometry scan as described above. Patients should be assessed for secondary causes of bone loss and followed up further if not improving on the 6-month follow-up scan, unless an alternative etiology has been identified.

If the patient enrolls directly into another relugolix clinical study upon completion of the Week 52 visit, then the follow-up bone densitometry scan at  $6 (\pm 1)$  months conducted under this protocol may be waived.

#### **6.5.2.7. Status of Menstruation Recovery**

If the first menstruation after the end of study treatment administration is observed before the Follow-up visit, the date of onset of the first menstruation is recorded in the eCRF. Patients whose menses has not resumed as of the Follow-Up visit for whom there is no explanation for

the lack of resumption (eg, medical procedure or medications) will be contacted again by telephone 3 (+0.5) months after the Follow-Up visit to determine if menses has resumed and will be asked about factors that may affect resumption of menses.

If the patient enrolls directly into another relugolix clinical study upon completion of the Week 52 visit, follow-up under this protocol to determine the status of menstruation recovery may not be required.

## 7. SAFETY CONSIDERATIONS

Study assessments of safety include adverse events, vital signs and weight, physical examinations, clinical laboratory tests, ECGs, and bone mineral density assessments.

### 7.1. Adverse Event Definitions

#### 7.1.1. Adverse Event

Adverse event: An adverse event is any unfavorable and unintended sign (including an abnormal laboratory finding), symptom, or disease (new or exacerbated) temporally associated with the use of a medicinal product, whether or not related to the medicinal product.

Events meeting the definition of an adverse event **include**:

- A worsening, excluding minor fluctuations, in the nature, severity, frequency, or duration of a pre-existing condition;
- Development of an intercurrent illness during the study;
- Development of symptoms that may or may not be related to the use of a concomitant medication or investigational product;
- Injury or accidents: If a medical condition is known to have caused the injury or accident, the medical condition and the accident should be reported as 2 separate medical events (eg, for a fall secondary to dizziness, both “dizziness” and “fall” should be recorded separately); and
- An investigational abnormality (eg, laboratory parameter, vital sign, ECG) only if the abnormality is considered clinically significant by the investigator based on at least one of the following criteria:
  - Induces clinical signs or symptoms;
  - Requires active intervention;
  - Requires interruption or discontinuation of study drug.

Events that **do not** meet the definition of an adverse event include:

- Medical or surgical procedures (eg, surgery, endoscopy, tooth extraction, transfusion); the condition that leads to the procedure is an adverse event;
- Pre-existing diseases or conditions present or detected before the start of study drug administration that do not worsen;

- Situations where an untoward medical event has not occurred (eg, planned hospitalization for an elective procedure, with elective defined as known or planned at the time of signing of the informed consent);
- Endometriosis-associated pain is not considered an adverse event in this study because it is being quantitatively measured as the primary efficacy endpoint.

Adverse events that occur during the study should be evaluated by the investigator and graded according to the National Cancer Institute Common Terminology Criteria for Adverse Events (CTCAE). Episodic adverse events, such as vomiting, or those that occur repeatedly over a period of consecutive days are “intermittent”. All other events are “continuous”. Additional information on detecting, documenting, and reporting adverse events and serious adverse events are provided below.

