### **5.10.3. Prohibited Non-Drug Therapies**

Surgical treatment of endometriosis is prohibited from the Week 24/Baseline visit until the patient's final study visit unless urgently needed for patient safety.

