### 7.1.2. Serious Adverse Event

A serious adverse event is any untoward medical occurrence that, at any dose:

- a. Results in death;
- b. Is life-threatening;  
NOTE: The term “life-threatening” in the definition of “serious” refers to an event in which the study participant was at risk of death at the time of the event. It does not refer to an event, which hypothetically might have caused death, if it were more severe. For example, drug-induced hepatitis that resolved without evidence of hepatic failure would not be considered life-threatening even though drug-induced hepatitis can be fatal.
- c. Requires hospitalization or prolongation of existing hospitalization;  
NOTE: In general, hospitalization signifies that the patient has been admitted to a hospital, independent of the duration of that hospitalization. Complications that occur during hospitalization are adverse events. If a complication prolongs hospitalization or fulfills any other serious criteria, the event is serious. When in doubt as to whether “hospitalization” occurred or was necessary, the adverse event should be considered serious. Hospitalization for elective treatment of a pre-existing condition that did not worsen from baseline is not considered an adverse event.
- d. Results in persistent or significant disability/incapacity;  
NOTE: The term disability means a substantial disruption of a person’s ability to conduct normal life functions. This definition is not intended to include experiences of relatively minor medical significance such as uncomplicated headache, nausea, vomiting, diarrhea, influenza, and accidental trauma (eg, sprained ankle) which may interfere or prevent everyday life functions but do not constitute a substantial disruption.
- e. Is a congenital anomaly/birth defect;
- f. Important medical events which jeopardize the patient and may require medical or surgical intervention to prevent one of the outcomes listed above. Examples of such events are invasive or malignant cancers, intensive treatment in an emergency room or at home for

---

allergic bronchospasm, blood dyscrasias or convulsions that do not result in hospitalization, or development of drug dependency or drug abuse.

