### 7.6. Serious Adverse Event Reporting

Using a Safety Reporting Form, all serious adverse events must be reported **within 24 hours of the study site personnel's knowledge of the event**, regardless of the investigator assessment of the relationship of the event to study drug.

The contact information for submission of serious adverse events, adverse events of clinical interest (defined in [Section 7.5](#)), and events of overdose is available on the Serious Adverse Event report form and is as follows:

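### Section 7.1.1 excludes endometriosis pain from adverse events without limit, which conflicts with neighbouring rules when worsened pain leads to hospitalization or an urgent procedure

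*Protocol*

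**What the plan says.** Section references follow Amendment 1.

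- Section 7.1.1 lists what does not count as an adverse event. The last item reads: "Endometriosis-associated pain is not considered an adverse event in this study because it is being quantitatively measured as the primary efficacy endpoint". The original protocol has the same sentence.
- The first item of that list removes procedures themselves from the definition, but adds that "the condition that leads to the procedure is an adverse event".
- The preceding list of what does count begins with "A worsening, excluding minor fluctuations, in the nature, severity, frequency, or duration of a pre-existing condition".
- Section 7.1.2 opens with "A serious adverse event is any untoward medical occurrence that, at any dose", and its third criterion is "Requires hospitalization or prolongation of existing hospitalization". The note to that criterion ends: "Hospitalization for elective treatment of a pre-existing condition that did not worsen from baseline is not considered an adverse event".
- Section 7.6 requires every serious adverse event to be reported within 24 hours, "regardless of the investigator assessment of the relationship of the event to study drug".
- Section 7.2.1 ends collection of adverse and serious adverse events at the follow-up visit about 30 days after the last dose, or earlier if certain things happen first. Surgical intervention for endometriosis is one of them. After that point, a serious event is to be reported only if the investigator judges it related to study drug.
- Section 5.10.3 prohibits surgery for endometriosis "unless urgently needed for patient safety". Section 5.7 foresees uncontrolled endometriosis pain despite the study analgesics and asks the site to contact the medical monitor.

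**The concern.** An efficacy extension can reasonably keep routine fluctuations of the target symptom out of the adverse event tables. The difficulty is that this exclusion has no upper limit. A woman admitted because her pelvic pain has worsened, or operated on urgently for it, falls under one rule that says her condition is an adverse event and another that says it is not.

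The incidence of adverse events is a named safety endpoint in a single-arm study planned at about 320 sites. If sites resolve the conflict in different ways, the count depends partly on which sentence each site read. The affected events are among the most clinically important treatment failures the study could observe.

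**Working it through.** No calculation applies, because the plan gives no figure on this point. The check sets the provisions side by side and applies them to two cases.

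**1. Is the exclusion bounded anywhere?** The other exclusions in 7.1.1 for existing disease and for hospitalization are bounded: existing conditions are left out only if they do not worsen, and admissions only if elective and already known or planned at consent. The pain item has no such bound, and 7.1.2, 7.2.1, 7.5 and 7.6 supply none. Section 7.5 shows that an explicit override is written where one is wanted: ALT or AST elevations at its threshold must be reported within 24 hours even when they are not serious.

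**2. Unplanned admission for worsened pain.**
- Worsening rule in 7.1.1: adverse event.
- Pain item in 7.1.1: not an adverse event.
- Section 7.1.2: an untoward occurrence requiring hospitalization, hence serious. The carve-out for elective treatment of a condition that has not worsened does not apply.
- Section 7.6: if serious, report within 24 hours.
- Against this, the hospitalization note in 7.1.2 says that in cases of doubt it is the adverse event that is to be treated as serious. That wording makes seriousness a property of an adverse event. A site that has concluded from 7.1.1 that there is no adverse event can stop there.

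**3. Urgent surgery with pain as the reason.**
- Procedures rule in 7.1.1: the condition behind the operation is an adverse event.
- Pain item in 7.1.1: it is not.
- Section 7.2.1: collection ends at the surgery. The pain began before the operation and so arguably falls inside the period, but the text does not say that the event leading to surgery is to be collected. A site recording it afterwards may see only the clause for related events, although 7.6 asks for reports whatever the relationship.

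**4. Does the stated reason cover these cases?** Section 9.4 builds the primary endpoints from average dysmenorrhea and nonmenstrual pelvic pain scores, together with analgesic use. The averages run over the 35 calendar days up to and including the last dose before the visit. They contain no record of an admission or an operation. Pain after the last dose lies outside every such window. The diary continues through follow-up, but those later scores do not enter the endpoint. Adverse event collection does continue for about 30 days, and in that interval the pain item removes the event from safety reporting while the endpoint does not pick it up.

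**5. Direction of the error.** Suppose N such serious events occur and a fraction p fall at sites that apply the pain item. The number reported is N × (1 − p). For any p from 0 to 1 this lies between 0 and N, so inconsistent reporting can lower the incidence and cannot raise it. The documents give neither N nor p.

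**The case against.** A reader might infer that these events escape serious adverse event reporting altogether, or that sites have no route to report them. The documents do not support that. Section 7.1.2 is worded around any untoward occurrence, not around events that have first qualified under 7.1.1. Its hospitalization carve-out is limited to elective care of a condition that has not worsened, and 7.6 then requires a report. Only the symptom of pain is excluded, so a site may report worsening endometriosis as a disease, and 7.2 prefers a diagnosis to a symptom. Read this way, a route exists. This part of the objection stands, and it reduces the finding to conflicting instructions.

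It can also be said that a specific exclusion overrides the general rules around it. That would settle adverse event status within 7.1.1, but it sharpens the conflict with 7.1.2.

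Severe pain also leaves traces elsewhere: contact with the medical monitor under 5.7, analgesic use in the eDiary, non-responder status when analgesic use increases, and the withdrawal reason on the eCRF. These are real, but none is a safety report and none enters the adverse event tables.

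Finally, the conflict is narrow. It bites only when pain itself is the reason for the admission or procedure, and 5.10.3 does not name pain as the reason for urgent surgery. In Amendment 1 the hospitalization note refers to admission, so an emergency visit alone does not meet that criterion.

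**Conclusion.** The point holds as a conflict of instructions that should be reconciled. The pain exclusion is categorical, it contradicts two rules in its own section, and it leaves 7.1.2 open to two readings for hospitalization or an urgent procedure driven by worsened pain. Different sites can defensibly report the same event differently, and any omission lowers the reported incidence.

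The size cannot be stated. The documents give no rate of pain-related admission or urgent surgery, so an event count would have no basis in them. The conclusion rests on the wording alone and assumes that at least some sites would treat the pain item as decisive.

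There is a version limit. Only the original and Amendment 1 texts of 7.1.1 are available. Amendment 2, which extends the open-label period to Week 104, breaks off in its synopsis, and Amendments 3 and 3.1 are not shown. Whether the operative protocol keeps the wording must be checked before acting. Nothing in the available text supports asking sites to enter past events retrospectively.

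**What to change.** Reconcile 7.1.1 with 7.1.2 and 7.6 by adding one sentence to the pain item: the exclusion does not apply when the event meets a seriousness criterion in 7.1.2, in which case it is recorded as an adverse event and reported under 7.6. The same sentence should say that non-serious endometriosis pain stays exempt, so that it no longer competes with the worsening and procedures rules.

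Align 7.2.1 by stating that the event leading to surgical intervention for endometriosis is collected even though collection otherwise ends there. The treatment-emergent period in 9.5 uses the same cut-off and should be read consistently with it.

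First check whether Amendments 2 to 3.1 already contain such wording. The text change is small, but a protocol modification needs ethics approval under 10.2.2 and must reach about 320 sites, so it is best carried by the next amendment and the eCRF completion guidelines. The study would receive a few more serious adverse event reports, and the reported incidence might be slightly higher. Treatment of patients and the efficacy analyses are unaffected.
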